- p. Eligible participants will complete a 30-minute pre-program (baseline) interview over the phone. They will be asked will be asked questions about things they do, physical activities they engage in, their social relationships with other residents in the community, and their health.
- q. Pre-program interviews will be administered through Qualtrics, and participants will be asked whether they know each of the other members of their intervention cohort. For each person they indicate knowing, they will be asked how much they respect that person on a 5-point Likert scale. The two most respected persons in each cohort will be invited via telephone to be a member of their respective cohorts' Advisory Committee. If either of the two persons declines the invitation, the 3rd most respected person will be invited. This will continue until two people agree to serve on the committee. During the Advisory Committee member recruitment call,

the role of being a committee member will be described (i.e., attend three committee meetings and remind other participants to attend intervention activities). Advisory Committee members will be asked to remind other cohort members to attend intervention activities only by making note of intervention activities during their regular interactions with the other participants (e.g., when see them in the hallway or in community common areas). They will not be asked to go out of their way to do this.

- r. Participants will be asked to wear a physical activity monitoring device (i.e., ActivPAL) on their thigh for 7 consecutive days after their pre- and post-program interviews. This is a small device that would be placed on your thigh with the help of a gentle adhesive. This device will continuously monitor their physical activity including activities like sitting, standing, walking and/or running. It will be recording the energy they had spent while performing the above-mentioned activities. When we retrieve this device from them, we will be looking at a number of values that tell us about their physical activity levels such as time spent sitting, standing, number of steps taken while walking and/or running, as well as energy spent per day.

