components from the post-intervention interviews will begin with an open-coding process to develop a codebook. This will involve the PI and Graduate Student Research Assistants (GSRAs) working on the program. Each person will read the text responses and independently develop a list of themes in the data. Next the team will meet to discuss the themes with a goal of reaching consensus on the list of themes and develop and agreed upon definition for each theme. This information will then be compiled into a codebook containing the list of themes/codes and their definition. Following this, the GSRAs will conduct axial coding. This will include associating specific passages of text with the themes/codes developed during the open-coding process. This will be done using qualitative data analysis software (NVivo). Inter-rater reliability (kappa) will be calculated for an initial sample of text passages coded by the GSRAs. If discrepancies exist, they will be discussed and the process repeated until kappa  $>0.80$ .

3. Power analysis: A power analysis was not conducted for the proposed analysis due to the descriptive nature of the proposed analyses, including analysis of open-ended text responses and descriptive analysis of process outcomes across the entire sample of study participants.
- d. AIM 3) Examine changes in secondary outcomes and differences in process and secondary outcomes by whether knew an AoC at baseline.
  - i. Hypotheses: The following hypotheses based on Social Contagion Theory and the Convoy Model of Social Relations will be tested: H3a-Network influence: Residents knowing 1+ committee members at baseline will participate in more intervention activities compared to those who do not. H3b-Pain as modifier: The network influence on participation will be greater among residents reporting more pain at baseline compared to those reporting less pain.
  - ii. Data analysis plan: Analysis for aim 3 will begin with descriptive analysis of secondary outcomes (physical function, PA, and pain) measured via self-report during both the pre- and post-intervention interviews. This will be done using statistical software (e.g., SPSS) and will include examination of variable frequencies, measures of central tendency, and sample variation. Next change scores will be created to document change in these measures from pre- to post-intervention and descriptive analyses conducted on these variables.

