- e. Analysis of accelerometry data: This study will use an accelerometer (activPAL) to measure physical activity among study participants. The activPAL is worn on the thigh continuously for 7-days. It has been shown to reliably measure sedentary time (including lying and sitting time) and activity intensity (i.e., estimates of energy expenditure) (Lyden et al., 2018). Raw data from the activPAL will be exported using activPAL provided software to a .csv file. The data will then be processed using an R-

package developed by developed specifically for activPAL data (Lyden et al, 2018). The data will be processed at the second level (1-second epochs). The same R-package will then be used to sum the following over the 7-day period I which the device was worn: 1) sedentary (i.e. sitting/lying) time (i.e., number of 1-second epochs of <1.50 metabolic equivalents); 2) light activity (i.e., standing and stepping) time (i.e., number of 1-second epochs between 1.50 and 2.99); and 3) moderate or higher activity time (i.e., number of 1-second epochs 3.00 or higher). The above data preparation and analysis steps will be applied to both the pre- and post-intervention accelerometry data. As a final step we will create changes scores in each of the three objectively measured indicators of activity (sedentary, light, and moderate or higher). Following creation of these variables, descriptive analysis will be conducted on these variable including examination of frequencies, measures of central tendency, and sample variation.

- f. Hypothesis testing: To test the proposed hypotheses (i.e., to test the presence of social network influence), mean differences and corresponding 95% confidence intervals in process measures (e.g., number of intervention activities that study participants participated in) and changes in secondary outcomes described above will be compared between study participants who knew one or more AoC at baseline and those who did not. Next, within these two groups we will stratify by pain measures to explore descriptively whether pain moderates network influence on outcomes.
- g. Power analysis: A power analysis was not conducted for this pilot study given the proposed small non-representative sample, which is likely to produce inaccurate estimates of effect size and their corresponding standard errors.

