#### IV. Foreseeable Risks to Participants

- a. 1) Risks Encountered During Data Collection: a) Rare and minimal risk of emotional distress from participating in survey interviews measuring psychosocial constructs. The interviewers conducting the pre- and post-program interviews will be trained to be sensitive to distress among participants. If a participant shows any signs of emotional distress the participant will be provided with a document listing the contact information of agencies they can consult with to receive counseling. b) skin irritation from Tegaderm adhesive used to waterproof and attach physical activity monitoring device (i.e., activPAL accelerometer) to study participants' thigh. Study team members will train participants on how to properly attach this device to

minimize irritation caused by improper attachment. There is also a minimal risk of an accidental breach or disclosure of identifying information. To prevent accidental breaches or disclosure of data collected, the study team will do the following:

- b. 2) In terms of the responses provided during the pre and post-program interviews:
  - i. We will use of an online computer program (Qualtrics) to enter the responses during the pre and post-program interviews.
  - ii. The program uses encryption and firewalls to ensure the data are not accessed by people outside of the study team.
  - iii. Participant's name and other identifying information (phone number and address) will not be entered into the program. We will identify you in the program with a study ID consisting of only numbers.
  - iv. Study data will be downloaded from the program and stored on a secure University of Michigan computer network where only study team members will have access.
  - v. Only study team members will have access to a password protected file that connect you to your study ID. Additionally this file will be stored on a secure University of Michigan computer network and accessed from password protected computers.
- c. 3) In terms of the data collected using the activity monitoring device:
  - i. Data collected via the activity monitoring device (activPAL) will only be accessible using a vendor provided docking station and software.
  - ii. The data will only be downloaded from the device using a password protected computer at the University of Michigan and stored on a secure computer network.

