  - iii. Participant data will be deleted from the device before the device is used again with another study participant.
  - iv. There is a serial number located on the device, which will be linked to a participant's unique study ID, which will be stored in the aforementioned password-protected file at the University of Michigan.
  - v. If the device is lost or stolen, it will not be possible for the data stored on the device to be linked back to a specific study participant. Protection of confidentiality will be ensured during required data and safety monitoring and reporting. Specifically, data will be presented in a blinded manner in the quarterly data and safety reports submitted to the study's locally appointed safety officer, and the study sponsors.

\*\*\*\*\*Ame00137652\*\*\*\*\* Protection of confidentiality will be ensured during required data and safety monitoring and reporting. Specifically, data will be presented in a blinded manner in the data and safety reports submitted to the study's sponsor.

IX. Subject payments or incentives

- a. Participants will receive \$10 for completing the study screening assessment and if they are eligible to participate, they will receive an additional \$25 for completing baseline and \$30 for completing the follow-up study assessments. Additionally, they will receive \$20 to wear an activity monitor for seven consecutive days at baseline and follow-up (\$10 for wearing it at baseline and \$10 for wearing it at follow-up), for a total of \$85 for participating in all parts of the study. Agents of change (AoC) will receive \$100 as a token of appreciation for their time to serve in this role, which will be provided following the committee's third (and last) meeting.
- b. The incentives are a token of appreciation of the time taken to complete data collection activities. Amounts are consistent with others similar in time. For agents of change (AoC), their incentive is a token of appreciation for the time to participate in multiple meetings as well as involvement in intervention administration (e.g., reminding others to attend meetings).
- c. Participants will only be compensated accordingly for completing the specific study activity. If they withdraw from the study, they will be compensated for the activities they completed prior to withdrawal.

X. Healthcare Treatments and Procedures

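### The activPAL change scores are built from raw epoch sums that are never divided by time worn, so unequal recorded wear would read as a change in activity

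*Combined protocol and SAP*

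**What the plan says.** Section III.e (Analysis of accelerometry data) has the device worn continuously for 7 days and the data processed in 1-second epochs. It then states: "The same R-package will then be used to sum the following over the 7-day period I which the device was worn". Three counts are summed: sedentary (below 1.50 METs), light ("number of 1-second epochs between 1.50 and 2.99") and moderate or higher (3.00 METs and above). The same steps apply before and after the intervention, and then: "As a final step we will create changes scores in each of the three objectively measured indicators of activity". These are to be described by frequencies, central tendency and variation.

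No passage gives these three variables a denominator, defines non-wear or a valid day, sets a minimum wear time, or says how a short recording is handled. The only per-day wording for the device is in II.r, which lists among its outputs "number of steps taken while walking and/or running, as well as energy spent per day". There it attaches to energy expenditure and does not define the III.e variables.

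The protocol does encourage full wear. On attachment, IV.a says: "Study team members will train participants on how to properly attach this device". IX.a pays participants "to wear an activity monitor for seven consecutive days at baseline and follow-up", and IX.c adds: "Participants will only be compensated accordingly for completing the specific study activity".

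**The concern.** A count of epochs depends on two things: how the participant spends the time, and how much time is recorded. Limiting the sum to time worn restricts what is counted but does not put participants or time points on a common footing. A change score built from two such counts mixes a change in behaviour with a change in recorded wear.

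At stake are the three activPAL change scores, the plan's only objective measures of activity in a study whose intervention aims to increase activity. H2a-c and H3a-b concern acceptance, attendance and participation and do not use these data. The comparison in III.f, by whether a participant knew an agent of change at baseline, is affected only if its secondary outcomes include the accelerometer variables. That is unclear, because III.d.ii describes "secondary outcomes (physical function, PA, and pain) measured via self-report".

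**Working it through.** The plan states no figure for this outcome that could be reproduced, so the check is direct arithmetic on its own definitions.

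**Inputs from the documents (III.a and III.e).** 7 days of wear; 1-second epochs; three MET bands that together cover recorded time; change score = follow-up sum minus baseline sum; planned sample of 24.

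**Assumption.** Days are similar within a participant, so a category's sum is proportional to the days recorded.

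**Full recording.** 7 × 86,400 = 604,800 epochs (168 h).

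**One wholly unrecorded day.** 86,400 / 604,800 = 14.3% of each sum.
- Lost at follow-up only: 6/7 − 1 = −14.3% with unchanged behaviour. The true rise that would be cancelled is 7/6 − 1 = 16.7%.
- Lost at baseline only: 7/6 − 1 = +16.7% of the recorded baseline with unchanged behaviour.

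**Range, with unchanged behaviour.** Apparent change = (follow-up days / baseline days) − 1.

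| Days recorded, baseline → follow-up | Apparent change in every sum |
|---|---|
| 7 → 7 | 0 |
| 7 → 6.5 | −7.1% |
| 7 → 6 | −14.3% |
| 7 → 5 | −28.6% |
| 6 → 7 | +16.7% |
| 5 → 7 | +40.0% |

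These percentages do not depend on how active the participant is.

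**Consistency check.** With equal recording the three change scores add to about zero, since time gained in one band is lost from another. With one day unrecorded at follow-up they add to 518,400 − 604,800 = −86,400 s = −24 h. Sedentary and active time then both appear to fall, which has no behavioural meaning. If all 24 participants contribute, one such participant moves the total of the three mean changes by −24 h / 24 = −1 h.

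**Effect of normalising.** Let S be a category's sum under full wear.
- Mean per valid day with six valid days: (6/7 × S) / 6 = S/7, the same as under full wear.
- Share of recorded time: (6/7 × S) / (6/7 × 604,800) = S / 604,800, unchanged.

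**Device off the thigh but still recording.** The plan does not say how this time is scored. Suppose it is scored below 1.50 METs, and take an assumed day of 19 h sedentary, 4 h light and 1 h moderate or higher. The total stays at 168 h. The table shows unworn time at follow-up only.

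| Unworn time | Sedentary | Light | Moderate or higher | After dividing by 7 calendar days |
|---|---|---|---|---|
| 0.5 day | +2.5 h | −2 h | −0.5 h | light −17.1, moderate or higher −4.3 min/day |
| 1 day | +5 h | −4 h | −1 h | light −34.3, moderate or higher −8.6 min/day |
| 2 days | +10 h | −8 h | −2 h | light −68.6, moderate or higher −17.1 min/day |

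Dividing by calendar days therefore does not remove this form of the artefact. Non-wear must be identified and excluded first.

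**The case against.** The strongest reply is that the artefact needs unequal wear, and the protocol works to prevent that. It specifies continuous wear, supplies a waterproof sleeve and adhesive (II.n), trains participants, collects the devices in person and pays for each wear period. No document fact shows that wear will differ systematically, and under full wear nothing is wrong. This stands, and it limits the weight of the point. It does not supply a rule for a recording that falls short.

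A second reply is that division by time worn is not the main gap: if the device is off but recording, the real omission is non-wear handling. This is right as far as it goes, and the remedy has to cover both.

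Third, the 7-day period could be read as a fixed, fully worn window, and the activPAL software or R package might screen non-wear by default. The documents state neither a rule for shorter recordings nor any such screening. Screening alone would still leave a sum without a denominator.

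Finally, the three sums together show the recorded time, so a gap could be spotted and rescaled later without new data. That is true of missing recording. It would not reveal off-body time scored as sedentary, and rescaling after seeing the data is weaker than a rule fixed beforehand.

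**Conclusion.** The concern holds. As written, III.e turns a difference in recorded wear into an apparent change in activity: −14.3% per sum for one whole day lost at follow-up, +16.7% for one lost at baseline, and zero with full wear at both time points. The percentages assume similar days and a wholly unrecorded day. They are illustrations, not estimates for this trial, because the documents give no rate of lost wear. For time off the body but recorded, even the direction depends on scoring that the plan does not state.

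The consequence is modest. This is a 24-person pilot, the III.e analysis is descriptive, no feasibility or participation hypothesis depends on it, and its use in III.f is uncertain. It is worth changing because the better measure costs little.

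**What to change.** In III.e, replace the 7-day sums with mean minutes per valid day, or percent of wear time, for each of the three categories. State how non-wear is identified and exclude it. Apply one prespecified valid-day rule and minimum number of valid days identically at both time points, with thresholds chosen and stated by the sponsor. Build the change scores from these values and report the number of valid days at each time point.

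The cost is a little processing code on data already being collected, and possibly a participant or two with low wear dropped from this analysis. The measure assumes that lost days resemble recorded days. Under full wear, minutes per day is simply the planned sum, converted to minutes, divided by 7, so nothing is lost.

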- m. For those who are eligible to participate, the study team will set up: 1) a day/time for a 30-minute pre-program interview administered over the telephone; and 2) before the interview, a day/time for the study team to make a visit to the housing community to drop off study materials and obtain signed consent for the study. For those screened to participate on-site, this informed consent process will occur directly after the screening interview. At the time of the in-person visit, the study team member will go over the consent form with the participant and answer any questions the participant may have. The participant will then be asked to print their name, sign and date the informed consent document. The signed copy will be taken and kept with study records and the participant will be given an unsigned copy for keep for their records. Following this, the time and date for the participant's pre-program interview will be confirmed.
- n. The study materials will include a copy of the screening consent form for the participants to keep for their records, the \$10 in cash for completing the screening interview, a tablet, a tablet charger cord, an HDMI cable to connect the tablet to a larger screen, a pedometer, an ActivPAL physical activity monitoring device wrapped in a water proof sleeve, Tegaderm adhesive/tape to attach the device to participant's thigh, and a copy of the consent form to participate in the study for the participants to keep for their records. During this visit, the participants will be trained on how to use these devices.
- o. Participants will be provided with tablets and pedometers to use during the study. They will be asked to return the tablet upon completion of all study activities, but they can keep the pedometer. These materials will be hand-delivered to all participants after they are determined to be eligible to participate in the program, but before their pre-program interview. Pedometers will be used to track steps and help motivate and inspire participants to reach their activity goals. Following the first remote one-on-one meeting with the OT, the OT will provide each participating resident with a packet of educational materials, information that will be used and covered during group sessions and also include individual pedometer tracking sheets

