- s. Participants identified to be potential Advisory Committee members must sign a separate consent form to serve in this role. This signed consent will be obtained in-person when the study team returns to participants' homes to pick-up the ActivPAL devices following the initial 7-day of wear. A copy of this consent form will be given to the participant to keep for their records. All the participants serving in this role will receive \$100 in cash at the completion of the study. This money will be hand-delivered to them at the end of the program in-person when picking up the ActivPAL device following the post-intervention 7-day of wear and the tablets.
- t. Once two cohort members have agreed to serve on the Advisory Committee we will hold an Advisory Committee Kick-Off Meeting. During the meeting the following will be discussed with the Advisory Committee Members: 1) the best day and time for OT weekly group sessions; 2) what the role of Advisory Committee member entails; 2) any questions or concerns regarding the role, which includes: a) attending two additional committee meetings during weeks 3 and 5, and during these meetings provide feedback on how the program is going from their perspective; and b) reminding other cohort members to attend intervention activities. This will include making note of intervention activities only during their regular interactions with the other participants (e.g., when see them in the hallway or in community common areas). During this kick-off meeting the Advisory Committee Members will be instructed how to avoid coercive statements in their reminders. This will be facilitated by providing examples of both non-coercive and coercive statements.
- u. Participants will be asked to meet individually with the OT for 60-90 minutes via Zoom to evaluate the relationship between the participant and their apartment for engagement in safe mobility and activity; assess the participant's activity performance, satisfaction, and barriers to activity engagement; establish 3-5 short-term activity goals; and outline the beginning of an individualized home exercise program. This will include the OT providing guidance on use of the program provided pedometer and also demonstration of 1 or 2 exercises that can be performed safely

in the home. The participating resident will then be invited to briefly perform the activities demonstrated and feedback will be provided by the OT.

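### Section III.e leaves out the step count named in II.r and pools standing with stepping, so standing replaced by walking below 3.00 METs shows on none of the three device outcomes

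*Combined protocol and SAP*

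**What the plan says.** Section II.r (Methodology) tells the reader what will be examined once the activPAL is retrieved: "time spent sitting, standing, number of steps taken while walking and/or running, as well as energy spent per day". Sitting, standing and steps appear there as separate values.

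Section III.e (Analysis of accelerometry data) processes the recording in 1-second epochs and sums three quantities over the 7 days of wear. The first is "1) sedentary (i.e. sitting/lying) time (i.e., number of 1-second epochs of <1.50 metabolic equivalents". The second is "2) light activity (i.e., standing and stepping) time (i.e., number of 1-second epochs between 1.50 and 2.99". The third is time at 3.00 METs or above. The plan then states that "we will create changes scores in each of the three objectively measured indicators of activity (sedentary, light, and moderate or higher". Descriptive analysis follows on those variables, and III.f compares changes in secondary outcomes between participants who did and did not know an agent of change at baseline.

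On the intervention side, II.o says: "Pedometers will be used to track steps and help motivate and inspire participants to reach their activity goals". The OT's first individual meeting is to "establish 3-5 short-term activity goals" (II.u), and each group session ends with chair rising and walking in place (II.v). Section IV.d describes the activity involved as low to moderate in intensity.

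**The concern.** The methods section and the analysis section do not match. Steps are named as a value to be looked at, participants follow their own steps on a pedometer with tracking sheets, and the activPAL records steps before and after the programme. Yet no analysis uses them.

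The omission matters more because of how the light category is built. Standing and slow walking fall in the same category, so a participant who moves time from one to the other leaves that category's total unchanged, and the other two totals as well. A step count, or a separate stepping time, is what would distinguish the two, and III.e contains neither. Aim 3 is to examine change in secondary outcomes, physical activity among them. The device data therefore have a blind spot for one kind of change in walking, and it carries through to the comparison in III.f.

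**Working it through.** The documents give no effect size, standard deviation or power figure for the device outcomes, so there is no stated result to reproduce. The check applies III.e's own cut-points to a worked swap of standing for walking.

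**Inputs from the documents**
- Categories (III.e): sedentary below 1.50 METs; light 1.50 to 2.99; moderate or higher from 3.00.
- Epoch length 1 second, summed over 7 days (III.e).

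**Assumptions, not in the documents**
- 30 min/day of standing replaced by walking, with the standing minutes contributing no steps.
- Standing scored at 1.6 METs, with 1.4 METs as a sensitivity value.
- Walking at 2.0 to 3.5 METs.
- Cadence 60 to 100 steps/min.

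**Epochs moved**

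Minutes per day × 60 × 7 = 30 × 60 × 7 = 12,600 one-second epochs.

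**Change in each device outcome over 7 days**

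| Standing scored | Walking scored | Sedentary | Light | Moderate or higher |
|---|---|---|---|---|
| 1.6 | 2.0 to 2.99 | 0 | −12,600 + 12,600 = 0 | 0 |
| 1.6 | 3.0 to 3.5 | 0 | −12,600 | +12,600 |
| 1.4 | 2.0 to 2.99 | −12,600 | +12,600 | 0 |
| 1.4 | 3.0 to 3.5 | −12,600 | 0 | +12,600 |

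Only the first row gives zero on all three outcomes. It needs two conditions together: standing scored inside the light band, and walking kept below 3.00 METs. The first agrees with III.e's own label for the light category. It is not fully settled, though, because III.e describes the sedentary and light categories both by posture or activity and by MET cut-point, without saying which governs.

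If the time replaced is sitting (below 1.50 METs), sedentary time falls by 12,600 epochs and light or moderate-or-higher time rises by the same amount, so that change is seen.

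**What a step count would show in the first row**
- Per day: 30 × 60 = 1,800 steps to 30 × 100 = 3,000 steps.
- Over 7 days: 1,800 × 7 = 12,600 steps to 3,000 × 7 = 21,000 steps.

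The step gain depends on cadence and minutes, not on the MET category, so it would be the same in every row.

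**The case against.** The strongest reply is that the mismatch is small and that several inferences from it go too far. Four readings may tempt a reader, and the documents do not support them.

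- *Any replacement of standing by walking goes unseen.* It does not. Walking at 3.00 METs or more moves time out of the light category, and IV.d allows for moderate activity.
- *Steps are the goal that the pedometer serves.* No step target is stated. The pedometer tracks steps in support of activity goals, and those are individual goals set with the OT. The sessions also cover mobility, pain management and energy conservation.
- *A pre-specified outcome has been removed.* II.r is a description of the device, and its list is introduced as examples: "such as time spent sitting, standing, number of steps taken". Standing time and daily energy are absent from III.e in the same way.
- *The trial would miss the behaviour change it is designed to produce.* The stated process and network hypotheses (H2a to H2c, H3a and H3b) concern acceptance, attendance and participation. Physical activity is also measured by self-report with its own change score (III.d.ii), and shifts from sitting to activity show in the existing categories.

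It is also fair to say that III.e gives a reason for its choice, citing evidence that the device measures sedentary time and intensity reliably, and that it says nothing comparable about steps. The 30 min/day swap is illustrative; nothing in the documents shows how common it would be.

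All of this limits the weight of the point. It does not remove it. II.r and III.e still disagree about steps, the pooling of standing with stepping is explicit, and the documents do not say that the self-report measures steps.

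**Conclusion.** The point holds in a limited form. Section III.e omits the step count that II.r says will be examined. Because it also pools standing with stepping, replacing standing with walking below 3.00 METs yields zero change on every device outcome, provided standing is scored at 1.50 to 2.99 METs. Under the assumed 30 min/day and 60 to 100 steps/min, the unreported change would be 1,800 to 3,000 steps/day. How often such a swap occurs in these residents cannot be judged from the documents.

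Severity is minor. This is a descriptive feasibility pilot of 24 participants, the device measures are secondary, and other shifts in activity remain visible. What justifies a change is that the inconsistency is real and that closing the gap needs no new data.

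**What to change.** In III.e, add mean steps per day from the same activPAL recordings, before and after the intervention, as a descriptive device outcome with its own change score. Include that change score among the secondary-outcome changes compared in III.f. Keep the three intensity outcomes as they are; steps need no priority over them.

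At the same time, align the other values listed in II.r with III.e: either add standing time and daily energy as descriptive variables, or state in II.r that they are recorded but not analysed.

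The cost is one more derived variable and one more mean difference with its 95% confidence interval in a pilot without a power analysis, to be read descriptively like the rest. No extra visit, device or participant burden is involved.
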